## 5) Inclusion and Exclusion Criteria\*

### **Inclusion Criteria:**

- 1) age 18-65 years;
- 2) diagnosis of schizophrenia or schizoaffective disorder;
- 3) stable dose of the current antipsychotic drug for at least one month;
- 4) well established compliance with outpatient treatment per treating clinician's judgment;
- 5) able to complete the cognitive assessment battery (must be English speaking);
- 6) Female subjects will be eligible to participate in the study if they are of non-childbearing potential or of child-bearing potential and willing to practice appropriate birth control methods during the study.

### **Exclusion Criteria:**

- 1) inability to provide informed consent, or for individuals with a legal guardian, inability to provide assent or a lack of informed consent from the legal guardian
- 2) current substance abuse
- 3) Subjects who are not on a stable dose of an antipsychotic medication for at least a month prior to enrollment
- 4) psychiatrically unstable per treating clinician's judgment
- 5) Uncontrolled medical condition including uncontrolled hypertension, diabetes, seizure disorder, severe cardiovascular, cerebrovascular, pulmonary, thyroid diseases, and gastroparesis.
- 6) history of ketoacidosis
- 7) currently taking insulin
- 8) currently taking meglitinides (repaglinide and nateglinide)

- 9) currently on immunosuppressant medication regularly including oral steroids; topical and inhalant steroids are allowed
- 10) currently on sulfonylurea drugs (e.g. glyburide)
- 11) Current, active chronic infection (including tuberculosis, HIV and hepatitis), malignancy, organ transplantation, blood dyscrasia, central nervous system demyelinating disorder, and any other known autoimmune or inflammatory condition
- 12) pregnant or breastfeeding.
- 13) prisoners
- 14) Exclusionary labs: eGFR < 35 ml/min

Hematology (CBC)	
Leukocytes	<2 or $>17.5 \times 10^3/\text{mm}^3$
Platelets	<75 or $>700 \times 10^3/\text{mm}^3$
Comprehensive Metabolic Panel	
Sodium	<1.1 times the lower limit ( $\leq 121.5$ ) or $>1.1$ times upper limit ( $\geq 159.5$ ) of the reference range
Potassium	<1.1 times the lower limit ( $\leq 3.15$ ) or $>1.1$ times upper limit ( $\geq 5.83$ ) of the reference range
Glucose	$>2$ times the upper limit ( $>198$ ) of the reference range
Blood Urea Nitrogen (BUN)	$>1.3$ times upper limit ( $>29.9$ ) of the reference range
Creatinine	$>1.3$ times upper limit ( $>1.69$ ) of the reference range
Total bilirubin	$>2$ times the upper limit ( $>2.4$ ) of the reference range
Aspartate amino transferase (AST)	$>3$ times upper limit ( $>120$ ) of the reference range
Alanine amino transferase (ALT)	$>3$ times upper limit ( $>120$ ) of the reference range
Alkaline phosphatase (ALP)	$>3$ times upper limit ( $>345$ ) of the reference range
Hemoglobin A1C	Patients with a value $\geq 9.0\%$

All exclusionary labs will be reviewed prior to administration of the study drug.

We will continue our recruitment efforts to assure a meaningful representation of women and minority populations.

Ages of subjects will range from 18-65 years. In recent years, there has been an increased use of antipsychotic agents in the younger population. The literature about antipsychotic treatment related to metabolic disturbances in children and adolescents is accumulating. The proposed studies included in this application will focus on the adult schizophrenia population. Only individuals in the range of 18-65 years of age will be included.

## 6) Study-Wide Number of Subjects\*

This is a single site study. We expect to enroll 110 subjects in this study with the goal of randomizing 70 subjects.

## **7) Study-Wide Recruitment Methods\***

This is a single-site study being conducted solely at UMass Medical School. For information on how potential subjects will be recruited, see section 24 (“Recruitment Methods”).

## **8) Study Timelines\***

The duration of an individual subject’s participation in the study will be 24 weeks. It is anticipated that 110 subjects will be enrolled, and 70 subjects will be randomized. This study received an extension to continue until our goal of 70 randomized patients is met. The investigators plan on completing primary analysis of the data within six months of the study’s completion.

## **9) Study Endpoints\***

### Primary Study Endpoint:

Improvement in negative symptoms as measured by the Scale for the Assessment of Negative Symptoms (SANS) total score.

### Secondary Study Endpoint:

Improvement in cognition as measured by the MATRICS Consensus Cognitive Battery (MCCB) composite score.

### Safety Endpoints:

An EKG will be conducted at the beginning and end of the study to assess safety. Vital Signs including blood pressure will be collected at every visit. Data on adverse events will be collected at every visit using the side effects questionnaires (SEQ and SEQabbrev) to assess safety and tolerability.

## **10) Procedures Involved\***

This is a 24-week, randomized, double-blind, placebo-controlled trial of exenatide weekly injection (2mg per dose) as an adjunctive therapy in 70 schizophrenia subjects to examine exenatide’s effects on negative symptoms, cognition and potential moderators or mediators of exenatide’s effects on negative and cognitive symptoms.

Informed consent will be obtained prior to the screening visit (see Section 30 “Consent Process”).

Screening visit: Fasting blood samples for glucose, insulin, HbA1c, lipid profile, comprehensive metabolic profile, CBC, high sensitivity CRP, eGFR and TNF- $\alpha$  will be obtained at the screening visit. Subjects will not receive study medication until all baseline labs have been completed, reviewed, and determined to fall within range. Potential subjects will undergo a diagnostic evaluation. Psychiatric diagnosis will be determined using the Structured Clinical Interview for DSM-IV Axis I Disorders (SCID). A medical evaluation, including weight, height, vital signs (heart rate, sitting, and standing blood pressures), a physical examination, and review of systems will be performed. The screening process includes a comprehensive review of medical history & evaluations, which is then reviewed by the PI before continuing with randomization. The study doctor discusses the patient's medical history with the patient, completes a review of systems, a physical exam, assesses the patient's overall health status, and reviews all available medical records, previous laboratory assessments and other relevant medical information in addition to the patient's self-report. Based on all of the information gathered, the PI then assesses the patient's eligibility for the study utilizing their clinical judgment. A urine pregnancy test will be performed on women of childbearing potential. Weekly reminders will be provided to the subject to use condoms or other appropriate birth control. The subjects will be given an appointment card for their next visit which will also provide a reminder for the use of appropriate birth control. In addition, a urine drug screening, and a 12-lead EKG will be performed. The screening visit will take about 2 hours. While the study team plans to complete all assessments in one study visit, it is likely that due to symptoms of psychosis, including avolition, apathy and cognitive disturbances subject may have inconsistent behavior and variable tolerance to screening procedures and assessment batteries. In such cases the subject may be called for an additional visit to complete the remaining procedures or they will be completed in the following visit. Following the screening visit, the subjects' primary care provider and/or psychiatrist will be notified of their participation in the study in order to adequately screen subjects, ensure that only eligible subjects are enrolled, and minimize subject risk. Ongoing subjects will be re-consented and informed of this notification during that time.

Baseline visit: The baseline visit will take about 5 hours to complete. Eligible subjects will come to the clinic for the baseline visit. Subjects will complete the clinical symptoms assessment, the extrapyramidal symptoms (EPS) assessment, and vital signs. On a separate day, subjects will come to the UMass Imaging Center at the university campus, or UMass Memorial MRI & Imaging Center at Shields MRI Imaging Suite to complete the brain MRI scans. Then the subjects will receive the study medication (either exenatide weekly injection (2mg per dose) or placebo injection). The UMass research pharmacy is responsible for randomization and preparation of study medication. The randomization is based on a double-blinded 1:1 ratio using permuted block randomization with randomly varying block size.

Follow-up visits (week 1-23): These visits will take about one hour to complete. Subjects will come to the clinic weekly to receive the study medication injection (exenatide or placebo); possible side effects will be assessed weekly. At week 6, 12, 18 visits, vital signs, the clinical symptoms assessment and the EPS assessment will be repeated; fasting blood samples for glucose, insulin, HbA1c, lipid profile, comprehensive metabolic profile, CBC, high sensitivity

CRP, eGFR and TNF- $\alpha$  will be obtained. In the event that research staff are unable to obtain a subject's blood sample at an indicated visit, subject's blood will be drawn in a week's time by a professional phlebotomist at UMass. In the event that a subject misses a visit where a routine blood draw is required, the subject will be scheduled to complete the routine blood draw prior to receiving the next dose of study medication. Once the lab results have been reviewed and signed off by the PI, the subject will be scheduled for their next study visit and will resume receiving the study medication.

Week 24 visit: This visit will take about 5 hours. The week 24 visit consists of vital signs, and side effects assessment. A 12-lead EKG will also be obtained during this visit. The clinical symptoms assessment and the EPS assessment will be repeated. Fasting blood samples for glucose, insulin, HbA1c, lipid profile, comprehensive metabolic profile, CBC, high sensitivity CRP, eGFR and TNF- $\alpha$  will be obtained. In the event that research staff are unable to obtain a subject's blood sample at an indicated visit, subject's blood will be drawn in a week's time by a professional phlebotomist at UMass. On a separate day, subjects will come to the UMass Imaging Center at the university campus, or UMass Memorial MRI & Imaging Center at Shields MRI Imaging Suite to repeat the brain MRI scans.

Clinical symptoms assessment: The clinical symptoms assessment includes: The Scale for Assessment of Negative Symptoms (SANS), the Positive and Negative Syndrome Scale (PANSS), the Clinical Global Impression Scale (CGI), the Calgary Depression Scale for Schizophrenia (CDSS), the Heinrichs Carpenter Quality of Life Scale (QLS), the Instrumental Activities of Daily Living Scale (IADL), and the MATRICS Consensus Cognitive Battery (MCCB).

Side effects/safety/EPS assessment: Possible side effects related to exenatide treatment will be monitored during each visit. Vital signs (blood pressure, pulse, temperature) and EPS will be evaluated at baseline, week 6, week 12, week 18 and week 24 using the Simpson-Angus Scale, the Barnes Akathisia Scale, and the Abnormal Involuntary Movement Scale (AIMS).

Bioassay: Routine blood tests (glucose, insulin, HbA1c, lipid profile, comprehensive metabolic profile, CBC, high sensitivity CRP, eGFR) will be performed at the UMass Core Lab. Plasma levels of IL-6 and TNF- $\alpha$  will be measured using enzyme-linked immunosorbent assay (ELISA) (R & D Systems) by Quest Diagnostics.

Structural MRI data acquisition, processing and analysis methods: To measure hippocampal volume at baseline and week 24, a structural MRI imaging examination will be performed at the UMass Advanced MRI facility on a Philips Achieva 3T system, or UMass Memorial MRI & Imaging Center at Shields MRI Imaging Suite on a GE 3T scanner. Segmentation of brain structures from T1-weighted 3D structural MRI data and estimation of structure volumes will be performed using the Freesurfer toolkit, which is freely available to the research community (<http://surfer.nmr.mgh.harvard.edu/>). This suite of methods uses a probabilistic brain atlas for

representation of spatial priors for brain labels (71). The current subcortical, cortical and white matter parcellation segmentation methods are fully automated. Each subject will result in a complete set of segmentations for volume and cortical surface. Each of these regions generates a volume; whole brain, cerebrum and white matter volumes are also available for normalization with respect to overall brain size.

**MRI Procedure:** Anatomic acquisitions will include: (1) a T2/PD double echo fast spin echo sequence, (2) a multi-flip angle 3D spoiled gradient echo (MPRAGE type) compatible with the UMASS/CANDI protocol, (3) an proton PRESS and single voxel MEscher-Garwood Point-REsolved Spectroscopy Sequence (MEGA-PRESS) (TE:68msec, TR:2000msec) MRS scans from the ACC, (4) a diffusion scan sequence that uses a standard single shot, spin echo, echo planar acquisition with diffusion weighting gradient pulses comprised of 32 diffusion-encoding directions with an additional baselineT2 weighted image and (5) Echo Planar MRI (EPI) / Functional MRI (fMRI) scan will measure brain fluctuations while at rest. Total scan time will be approximately 60 minutes. Post-processing will be performed with standard software (LCModel, Freesurfer, and FSL) to quantify the MRS metabolites, and regional gray and white matter structural properties in the brain.

A trained neuroradiologist associated with the MRI imaging center at University of Massachusetts Medical School will read the diagnostic MRI scans. In the event that there is a suspicious reading on the MRI the PI will be informed of this. The PI will share with the subject the findings and will facilitate in helping them determine what follow up care is needed and appropriate.

It is possible that a subject may not complete the MRI scan in the study either because the subject is not interested in this component or because it may not be appropriate (for example, claustrophobia or implanted metal in the subject's body). Only those subjects who qualify will complete the MRI scan throughout the study.

## **11) Data and Specimen Banking\***

Extra blood samples will be collected for future research related to schizophrenia. We will store samples for future genetic testing. These samples will be labeled with a unique study ID code. Only members of the research team will be able to derive an individual's identity from their study ID code. The key to the code is stored on secure server and can only be accessed through password-protected computer.

Extra blood samples will be drawn at Biotech One, Suite 100 or at Community Health link and stored in a -80°F freezer, which is located in a locked room at Biotech One.

While there are no definitive plans yet for use of these samples, the Principal Investigator plans to store these blood samples indefinitely after the study's completion. A log system will be put in place to ensure that only authorized research personnel have access to the samples. The PI will be held responsible for the safety and security of these samples. A separate IRB approval will be requested to utilize these stored samples in the future.

## **12) Data Management\***

All data management will be conducted in the research offices of the Biotech One building. Standard data forms for the clinical rating scales will be used for this project. Individual notebooks will be maintained for each subject that will include signed consent, letter to halfway house, subject information sheets, raw data from clinical rating scales, laboratory measurements and a study timetable or flow sheet for that subject. A study database will be created using the REDCap system. The data will be stored on a secure server in the UMass HIPAA-compliant data center with daily backup. The database will be designed by the PI and maintained by the PI and the research staff. Data entry will be performed by research coordinators and will be reviewed by the research manager and the PI for accuracy. Access to the database will be restricted by password. All data will be stored safely for 5 years.

There are no published data yet about exenatide's effects on clinical symptoms and cognition in the schizophrenia population. This study is intended as an initial test of efficacy. Repeated measures of clinical symptoms and cognitive performance will be analyzed in separate linear mixed models with fixed effects of visit, treatment group, baseline score, and visit x treatment and visit x baseline score interactions and random participant-specific intercepts and slopes. Potential confounding variables will be included as covariates. The effect of exenatide on 24-week change from baseline will be determined by the estimated regression coefficient of the visit x group interaction term. The sample of 60 evaluable subjects will have 80% power to detect an effect size of 0.74 based on a two-tailed t-test at alpha = 0.05.

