Baseline visit: Eligible subjects came to the clinic for the baseline visit. Fasting blood samples for glucose, insulin, HbA1c, lipid profile, comprehensive metabolic profile, CBC, high sensitivity C-reactive protein (hsCRP), and tumor necrosis factor α (TNF- α) were obtained. The subject completed the clinical symptoms assessment, the extrapyramidal symptoms (EPS) assessment, and vital signs. Then the subject received the study medication (either exenatide 2mg or placebo weekly injection). The randomization was based on a double-blinded 1:1 ratio using permuted block with randomly varying block size.

Follow-up visits (week 1-24): Subjects came to the clinic weekly to receive the study medication injection; possible side effects were assessed weekly. At week 6, 12, 18, 24 visits, vital signs, the clinical symptoms assessment and the EPS assessment were repeated; fasting blood samples for glucose, insulin, HbA1c, lipid profile, comprehensive metabolic profile, CBC, hsCRP, and TNF- α were obtained.

Clinical symptoms assessment: The clinical symptoms assessment included: The Scale for Assessment of Negative Symptoms (SANS), the Positive and Negative Syndrome Scale (PANSS), the Clinical Global Impression Scale (CGI), the Calgary Depression Scale for Schizophrenia (CDSS), the Heinrichs Carpenter Quality of Life Scale (QLS), the Instrumental

Activities of Daily Living Scale (IADL), and the MATRICS Consensus Cognitive Battery (MCCB).

EPS assessment: The EPS scales included: the Simpson-Angus Scale, the Barnes Akathisia Scale, and the Abnormal Involuntary Movement Scale (AIMS).

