Statistical analysis: Statistical analysis was performed using SPSS (version 24.0, IBM Corp, Armonk, NY, USA). Descriptive statistics were performed to summarize demographic and clinical characteristics of the study sample. Group comparisons were performed using independent samples t test for continuous variables and the Fisher exact test or Chi-square test for categorical variables. The outcome measures were repeated at different time points. Therefore, analysis of repeated measures using mixed models was performed to compare the change over time in outcome measures between the two treatment groups while controlling for potential confounding variables. The mixed model approach does not require subjects to have the same number of study visits or measurements and uses all available data instead of eliminating subjects with missing data, resulting in unbiased estimates of the model parameters when data are missing at random. Further, for those who completed 24-week treatment, analysis of covariance (ANCOVA) was used to compare change scores from baseline to week 24 between the two treatment groups controlling for potential confounding variables. For all analyses, a P value less than 0.05 (two-tailed) was used for statistical significance.

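### On the most natural reading of Section 12, the visit x group coefficient shows only how the SANS difference changes after week 6, and need not equal the week-24 effect it is said to give

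*Protocol*

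**What the plan says.** Protocol Section 12 (Data Management) specifies separate linear mixed models for the repeated measures, with "fixed effects of visit, treatment group, baseline score, and visit x treatment and visit x baseline score interactions and random participant-specific intercepts and slopes". It then names the quantity that carries the efficacy result: "The effect of exenatide on 24-week change from baseline will be determined by the estimated regression coefficient of the visit x group interaction term". The same paragraph gives the power statement, that "60 evaluable subjects will have 80% power to detect an effect size of 0.74 based on a two-tailed t-test" at alpha 0.05.

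The primary endpoint in Section 9 is "Improvement in negative symptoms as measured by the Scale for the Assessment of Negative Symptoms (SANS) total score", with no time point. The Section 12 sentence is therefore where the protocol ties the efficacy effect to week 24.

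SANS belongs to the clinical symptoms assessment, which is done at baseline and then as follows: "At week 6, 12, 18 visits, vital signs, the clinical symptoms assessment and the EPS assessment will be repeated", and again at week 24 (Section 10). The SAP's Procedures agree: "At week 6, 12, 18, 24 visits, vital signs, the clinical symptoms assessment and the EPS assessment were repeated".

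The SAP's statistical analysis paragraph does not repeat the single-coefficient rule and lists no model terms. It says only that "mixed models was performed to compare the change over time in outcome measures between the two treatment groups while controlling for potential confounding variables". It adds that "for those who completed 24-week treatment, analysis of covariance (ANCOVA) was used to compare change scores from baseline to week 24", again adjusting for possible confounders. Neither analysis is named as primary. Neither document says whether visit is numeric or a factor, which visit is the reference, or whether the week-0 score is a response as well as a covariate.

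**The concern.** When baseline score enters as a covariate and also interacts with visit, the usual responses are the post-baseline scores. A week-0 response row would simply be predicted by its own covariate. The group term is free, so it takes up any difference already present at the first post-baseline rating, at week 6. The interaction sees only what happens between weeks 6 and 24. The treatment difference at week 24 is the group term plus the interaction evaluated at week 24, and Section 12 never forms that sum.

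The named coefficient and the stated target are then different quantities, and the gap depends on the time course of the effect. A benefit that arrives early and persists would be understated, possibly to nothing. One that arrives late would be overstated. One that peaks early and partly fades could be reported with the wrong sign. Section 12 itself says that no data have been published on exenatide's symptom effects in this population, so none of these time courses can be ruled out from the documents.

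**Working it through.** **The plan's own figure.** Inputs from Section 12: 60 evaluable subjects, effect size 0.74, two-tailed alpha 0.05; allocation 1:1 from Section 10, so 30 per arm. A two-sample t-test by the noncentral t distribution gives power 80.5%. The stated 80% reproduces.

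**Assumptions for the check.** The documents give no time course, SD or correlation. I take a true benefit of 0.74 SD at week 24, except in the fading case, where it is 0.37. Data are complete, and benefit is written as positive.

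**Formulas.** Let d(t) be the true group difference at week t.

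- (a) No week-0 row, numeric visit. The interaction is the least-squares slope of d over weeks 6, 12, 18, 24. The mean week is 15, the deviations are -9, -3, 3, 9, and Sxx = 81 + 9 + 9 + 81 = 180. Scaled estimate = 24 x sum[(t - 15) d(t)] / 180.
- (b) No week-0 row, factor visit referenced to week 6. Week-24 interaction = d(24) - d(6).
- (c) Week-0 row with d(0) = 0, numeric visit. The mean week is 12 and Sxx = 144 + 36 + 0 + 36 + 144 = 360. Scaled estimate = 24 x sum[(t - 12) d(t)] / 360.
- (d) Week-0 row, factor visit referenced to week 0. Week-24 interaction = d(24) - d(0) = d(24).

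**Worked cases.**

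- Half by week 6, then linear, under (a): slope = (0.74 - 0.37)/18 = 0.02056; x 24 = 0.493.
- Held from week 6: under (a) the deviations sum to zero, giving 0. Under (c), 0.74 x (-6 + 0 + 6 + 12) = 8.88; 8.88/360 x 24 = 0.592.
- Late onset (0, 0, 0.37, 0.74) under (a): 3 x 0.37 + 9 x 0.74 = 7.77; 7.77/180 x 24 = 1.036.
- Fading from 0.74 to 0.37: under (a), slope = -0.37/18, x 24 = -0.493. Under (c), -6 x 0.74 + 0 + 6 x 0.493 + 12 x 0.37 = 2.96; 2.96/360 x 24 = 0.197.

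| Time course | True week 24 | (a) | (b) | (c) | (d) |
|---|---|---|---|---|---|
| Linear from zero | 0.74 | 0.74 | 0.56 | 0.74 | 0.74 |
| Half by week 6, then linear | 0.74 | 0.49 | 0.37 | 0.69 | 0.74 |
| Three-quarters by week 6, then linear | 0.74 | 0.25 | 0.19 | 0.64 | 0.74 |
| Complete by week 6, held | 0.74 | 0 | 0 | 0.59 | 0.74 |
| Late: 0, 0, 0.37, 0.74 | 0.74 | 1.04 | 0.74 | 0.74 | 0.74 |
| 0.74 at week 6, fading | 0.37 | -0.49 | -0.37 | 0.20 | 0.37 |

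With complete data, random intercepts and slopes do not change the expected values in (a) and (c). They affect precision only.

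**What this does to the test.** Under (a), assume further an SD of 1 and equal correlation r between visits, and condition on baseline. The standard error of the scaled coefficient is 24 x sqrt[(1 - r)/180 x 2/30], which is 0.386 at r = 0.3 and 0.207 at r = 0.8. With 57 df, power across r = 0.3 to 0.8 is 47-94% for linear growth, 24-65% for half by week 6, 10-22% for three-quarters by week 6, and 5% (the type I error rate) for a held benefit.

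**Does adding the group term suffice?** Not if visit stays numeric. For a plateau from week 12 (0.37, 0.74, 0.74, 0.74), the slope is 0.0185 per week and the group term at week 0 is 0.6475 - 15 x 0.0185 = 0.37. Group plus 24 x slope = 0.37 + 0.444 = 0.81, not 0.74. With visit as a factor the week-24 contrast equals d(24) whatever the shape.

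**The case against.** The strongest reply is that the defect depends on a coding the documents leave open. The target is expressed as change from baseline, and the SAP speaks of change over time. Both can be read as putting week 0 on the response axis. The loss under numeric visit is then much smaller (0.59 of 0.74 for a held benefit), the sign reversal in the fading case disappears, and a factor visit referenced to week 0 has no loss. This stands as a limit on certainty but does not clear the plan. The baseline and visit x baseline terms favour post-baseline responses, and the single coefficient with random slopes favours numeric visit, so the fully correct coding is not the most natural reading. A factor visit would also produce several interaction coefficients, and none is singled out.

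Second, the SAP's ANCOVA does compare change from baseline to week 24. A reader might therefore infer either that the problem is cured or, going the other way, that a week-24 effect would go unexamined. Neither follows. The ANCOVA targets the right quantity, but only in completers and without being named primary.

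Third, gradual benefit is at least as compatible as rapid benefit with the neuroprotective rationale in Section 4, and linear growth gives the right expected value under numeric visit. That is fair, but the plan neither states nor justifies linear growth.

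A reader might also infer that the 80% power figure is wrong, or that the coefficient always understates. The first is not supported: the figure is correct for the t-test it names. The second is false, because late onset gives 1.04 for a true 0.74.

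**Conclusion.** The point holds in conditional form. On the most natural reading of Section 12, the named coefficient is not the effect on 24-week change. It is a measure of how the difference moves after week 6, and with numeric visit it is generally a valid stand-in only if the benefit grows linearly from zero. For an assumed 0.74 SD benefit at week 24, the expected estimate runs from 0 to about 1.04 across the time courses examined. For a benefit fading to 0.37 it is -0.49. With a week-0 response row and numeric visit the range narrows but a held benefit is still estimated at 0.59. Only a factor visit referenced to week 0 returns the true value throughout.

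These sizes rest on assumed time courses and complete data, and the power ranges also on an assumed equal correlation of 0.3 to 0.8. The documents do not show which coding was used, so it cannot be said that the trial's reported effect is biased or that a real benefit was missed. What can be said is that neither document establishes that the stated coefficient equals the stated effect. This should be fixed. Confidence is medium because of the open coding.

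**What to change.** In Section 12 and in the SAP, define the primary estimate as the model-based treatment difference in SANS total at week 24, two-sided 0.05, with visit as a factor. Either of two forms will do: group plus visit x group evaluated at week 24 with baseline score as a covariate, or the week-24 interaction in a model that has a week-0 response row as the reference level. State which one is used. There is no need to prohibit a week-0 row, and the covariance structure can be left to the trial statistician.

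Use the same contrast for the MCCB composite. Name this analysis as primary in the SAP and label the completer ANCOVA as supportive. Leave the power statement as it is, and do not add a new power figure.

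The cost is one contrast statement and a short re-analysis, with no new data or patients. Because the SAP is written in the past tense, this is a change to the definition of the primary effect and should be recorded as one. State the visit coding and baseline handling of any model already run, and say whether the change was made before unblinding. If it was made after, report the coefficient that Section 12 now names alongside the week-24 contrast.
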